12.3.2 Tobacco and nicotine containing products use history and habits

All data collected at Screening about tobacco and nicotine containing products use history and habits as described in Table 11 will be summarized.

Table 14: Tobacco and nicotine containing products use history – List of Questions

1. Have you smoked for at least the past 3 consecutive years?
2. How many years have you smoked?
3. On average, how many cigarettes per day have you smoked over the last 3 months?
- 3b. Of these, on average, per day, how many were menthol cigarettes?
4. On average, how many cigarettes per day have you smoked since you started smoking?
5. Is the variant of brand you are currently using most often menthol or not
6. Have you used any of the following tobacco/nicotine containing products over the last year?
 - a) Pipe
 - b) Hookah
 - c) Heatnotburn Products
 - d) e-cigarette
 - e) Snuff or chewing tobacco

f) Nicotine Replacement Therapy (e.g., patches, gum)

6b Have you used any of the following tobacco/nicotine containing products over the last 7 days?

- a) Pipe
- b) Hookah
- c) Heatnotburn Products
- d) e-cigarette
- e) Snuff or chewing tobacco
- f) Nicotine Replacement Therapy (e.g., patches, gum)

7. During your working hours, on average, how often can you take a break for smoking a cigarette?

8. What are three occasions on which you were using P3P the most during the last month?

- a) At home, indoors
- b) At home, outdoors (e.g. garden, balcony)
- c) In areas where I don't normally smoke (e.g. at my desk at place of work)
- d) In a designated outdoor smoking area at my place of work
- e) In a designated indoor smoking area at my place of work
- f) In a designated indoor or outdoor smoking area (e.g. terrace) in a bar, restaurant, cafe or nightclub
- g) In public areas (e.g. in the street, in a park)
- h) At a friend or colleague's home
- i) At a family member's home
- j) In the car

Answers to questions 2 to 4 will be considered continuous, all others will be summarized using frequencies. Data will be listed and summarized as presented in the below outputs:

TFL number	Title
TABLES	
15.2.7.1	Summary of Tobacco and nicotine containing products use history and habits -(Q2 to Q4) - Safety Population
15.2.7.2	Summary of Tobacco and nicotine containing products use history and habits -(Q1, Q5-Q8) - Safety Population
LISTINGS	
15.1.7.1	Listing of Tobacco and nicotine containing products use history and habits- Safety Population

12.3.3 Other Data

Other data collected at Screening and/or Admission prior to first P3P product use will be listed by P3P variant and subject. These data are as follows:

- Urine cotinine test
- Urine pregnancy test
- Chest x-ray

- Urine drug screen
- Serology
- Alcohol breath test
- Product Test and Demonstration

ECG, Spirometry, obtained at Screening and/or admission will be presented with data obtained post P3P product use.

The data will be presented in the below outputs:

TFL number	Title
LISTINGS	
15.1.7.2	Urine cotinine test, Urine pregnancy test, Chest x-ray, Urine drug screen, Alcohol breath test, Serology – Safety Population
15.1.7.3	Product Test and Demonstration – Safety Population

12.4 Extent of Exposure (Product Consumption)

The number and percentage of subjects using ≤ 5 /Day, $>5-10$ /Day, or >10 P3P /Day P3P products per product exposure period (Table 7) and overall will be summarized per product variant for the safety population (By Variant and Total) and by Sex.

Descriptive statistics of the daily product use considered as a continuous variable will be presented as well.

Details of the exposure to product during the on-site period use will be listed by P3P variant for the Safety population.

Listings of average daily exposure by visit period will be provided.

The data will be presented in the below outputs:

TFL number	Title
TABLES	
15.2.8.1	Descriptive Statistics of Product Exposure Category by Period - Safety Population
15.2.8.2	Descriptive Statistics of Product Exposure Category by Period and by Exposure Category - By Sex - Safety Population
15.2.8.3	Descriptive Statistics of Product Exposure by Period - Safety Population
15.2.8.4	Descriptive Statistics of Product Exposure by Period - By Sex – Safety Population
LISTINGS	
15.1.8.1	Average Daily Exposure to Product by Period – Randomized Population

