#### 3.2 Secondary Objectives and Endpoints

1. To evaluate the pharmacodynamic effects (subjective effects and related behavioral assessments) of the two P3P variants.

Endpoints:

- Visual Analogue Scale (VAS)-craving assessment in parallel with PK assessment on Day 1 and Day 30;
- Sensory Questionnaire on Day 1 and Day 30;
- ABOUTTM-Product Experience Questionnaire on Day 1 and Day 30.

2. To assess product acceptance and puffing/inhalation behavior of both P3P variants

Endpoints:

- Product acceptance questionnaire on Day 1 and Day 30;
- Puffing/inhalation behavior question:
  - Evaluated by site staff on Day 1 and Day 30
  - Answered by subject on Day 2, Day 7, Day 15, Day 22 and Day 29.

3. To assess nicotine/tobacco product use.

Endpoints:

- Number of P3P, cigarettes, e-cigarettes or/and other nicotine/tobacco product use from Day 1 to Day 30;
- Change in the number of cigarettes used throughout the study as compared to the reported number at Screening.

---

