### 12.3 Analysis Populations

Pharmacokinetic, pharmacodynamics, product acceptance, puffing/inhalation behavior endpoints will be analyzed using the PK population by actual product exposure and overall. Nicotine/tobacco containing product use, tobacco and nicotine containing product dependence, and CYP2A6 activity will be analyzed using the randomized population by actual product exposure and overall. Exposure to harmful and potentially harmful constituents will be analyzed using the randomized population. Safety will be analyzed using the safety population by actual product exposure and overall.

Actual product use exposure categories will be further defined in the SAP. Additional populations for sensitivity analysis could be defined in the SAP.

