9 CHANGES FROM THE PROTOCOL SPECIFIED STATISTICAL ANALYSIS

The following changes with respect to the analysis populations were made in the SAP compared to the Protocol:

- Changes regarding Population of Subjects to be Used for Different Endpoints

Endpoints	Protocol	SAP
Pharmacodynamics (VAS craving, Sensory questionnaire, ABOUT™ -Product Experience)	PK	Randomized
Product Acceptance	PK	Randomized
Puffing Inhalation Behavior	PK	Randomized

In addition, results for the 2 variants combined will not be reported except for data collected at baseline.

- Changes regarding Analysis Model for PK and AUC for VAS craving score

In the protocol, an ANOVA model with sex and product exposure category as factors was anticipated to be used to compare PK parameters and AUC for VAS craving score between variants at Day 30. The ANOVA model was replaced by an ANCOVA model with sex and product exposure category as factors and Day 1 value as covariate.

No Day 1 comparisons will be performed. Within-group comparisons Day 30 versus Day 1 will also be performed in an ANOVA model with sex and product exposure category as factors.

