12.1.3 Descriptive Statistics

All data will be presented in listings.

All endpoints will be summarized with descriptive statistics including number of subjects (n), number and percent of subjects with missing data, arithmetic means, 95% confidence intervals of the mean, and standard deviations (SD), median, first and third quartiles, minimum and maximum. Change from baseline will be added to the summary statistics when applicable.

For log normally distributed endpoints geometric mean, 95% confidence intervals of the geometric mean, geometric CV will be presented instead of arithmetic mean, 95% confidence intervals of the mean, and SD and percent change from baseline will be presented instead of change from baseline.

Categorical variables will be summarized by frequency statistics (number and percentage). For endpoints relating to sampling times (e.g., tmax) only median, first and third quartiles, and minimum and maximum will be presented.

Summary statistics and statistical analyses will be performed for subjects included in the relevant analysis population. For the calculation of summary statistics and statistical analysis, unrounded data will be used.

Summaries on Safety population will be produced by randomization group and overall, including the available data from subjects who tested the product but were not randomized.

The following product labels and descriptions will be used for the TFLs (Table 12):

Table 12: Product Labels

Randomization Group/P3P Variant	Format used in TFLs	Order in TFLs
P3P-1mg	P3P-1mg	1

P3P-2mgP3P-2mg

2

The following stratification labels (Table 13) for the TFLs will be used:

Table 13: Stratification Labels

Stratification Factor	
Sex	Male
	Female
Product Exposure Category	≤ 5 P3P/Day
	>5-10 P3P/Day
	>10 P3P/Day

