12.5.4 Nicotine/Tobacco product use

The following variables:

- Average Cigarettes smoked per day during a period
- Change from baseline in average number of cigarettes used per day during a period

- Average Heat not burn and/or smokeless tobacco products used per day during a period
- Average Other tobacco products (pipe, cigar, cigarillos, chewable...) used per day during a period
- Average occasions Electronic Cigarette used per day during a period
- Percentage (%) of P3P used during a period with % P3P = $100 * \text{number of P3P} / (\text{number of P3P and CC})$
- Percentage of subjects having used any Nicotine Replacement Therapies during a period

will be summarized in a descriptive manner for each period being the time interval between 2 consecutive visits and also for the complete exposure period.

The data will be presented in the below outputs:

TFL number	Title
TABLES	
15.2.18.1	Descriptive Statistics of Average Cigarettes smoked /day - By Period – Safety Population
15.2.18.2	Descriptive Statistics of Average Cigarettes smoked /day By Product Exposure Category (≤ 5 P3P/day, $> 5 - 10$ P3P/day, > 10 P3P/day) - By Period – Safety Population
15.2.18.3	Descriptive Statistics of Change from Baseline in Average Cigarettes smoked /day - By Period – Safety Population
15.2.18.4	Descriptive Statistics of Average Heat not burn and/or smokeless tobacco products used /day - By Period – Safety Population
15.2.18.5	Descriptive Statistics of Average Other tobacco products (pipe, cigar, cigarillos, chewable...) used/day - By Period – Safety Population
15.2.18.6	Descriptive Statistics of Average occasions Electronic Cigarette used /day - By Period – Safety Population
15.2.18.7	Descriptive Statistics of Percentage (%) of P3P use - By Period – Safety Population
15.2.18.8	Percentage of subjects having used any Nicotine Replacement Therapies – By Period
LISTINGS	
15.1.18.1	Listing of Nicotine/Tobacco product use - By Period

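### The SAP moves the product-use endpoint from the protocol's randomized population to the Safety population without declaring it, so never-randomized product testers enter the Total column

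*SAP*

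**What the plan says.** Protocol 3.2 defines the endpoint under secondary objective 3: "Number of P3P, cigarettes, e-cigarettes or/and other nicotine/tobacco product use from Day 1 to Day 30", together with the change in cigarettes from Screening. Protocol 12.3 fixes the population: "Nicotine/tobacco containing product use, tobacco and nicotine containing product dependence, and CYP2A6 activity will be analyzed using the randomized population".

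SAP 12.4 states that the numbers of subjects in the three P3P-per-day categories "will be summarized per product variant for the safety population (By Variant and Total) and by Sex". All four of its tables (15.2.8.1 to 15.2.8.4) are titled Safety Population, but the listing behind them, 15.1.8.1, is titled "Average Daily Exposure to Product by Period – Randomized Population". SAP 12.5.4 covers cigarettes and other products. Tables 15.2.18.1 to 15.2.18.7 carry the Safety label, for example "Descriptive Statistics of Change from Baseline in Average Cigarettes smoked /day - By Period – Safety Population", and Table 15.2.18.8 names no population.

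SAP 12.1.3 adds that Safety summaries are given by randomization group and overall, "including the available data from subjects who tested the product but were not randomized". SAP 9 has an entry headed "Changes regarding Population of Subjects to be Used for Different Endpoints", which covers only pharmacodynamics, product acceptance and puffing behavior. The same section says that the two variants will not be reported combined, except for baseline data.

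**The concern.** A reader who relies on SAP 9 would conclude that product use is still analyzed as the protocol says. It is not. The new population also brings in people for whom the endpoint does not exist. A subject who tried P3P on Day -1, declined to continue and left was never given a variant or a diary and was never in the Day 1 to Day 30 period.

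The overall summary of use and switching would then depend partly on how many people rejected the product at the test. It would also rest on a different N from the dependence, CYP2A6 and biomarker tables (SAP 12.5.5 to 12.5.7), which are on the Randomized population and will be read beside it. Tables 15.2.8.3 and 15.2.18.3 are among the topline results in SAP 13.2, so they will be seen early. The usual answer, that extent of exposure is a safety display, does not reach far enough. SAP 12.5.4 does not tabulate average P3P per day, so SAP 12.4 is the only place where the P3P count in the endpoint is summarized.

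**Working it through.** **1. Populations side by side**

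| Output | Protocol 12.3 | SAP | In SAP 9? |
|---|---|---|---|
| P3P consumption, Tables 15.2.8.1–15.2.8.4 | Randomized | Safety | No |
| Listing 15.1.8.1 | Randomized | Randomized | Not needed |
| Cigarettes, other products, % P3P, Tables 15.2.18.1–15.2.18.7 | Randomized | Safety | No |
| Nicotine replacement, Table 15.2.18.8 | Randomized | None named | No |
| Dependence and CYP2A6 tables (SAP 12.5.6, 12.5.7) | Randomized | Randomized | Not needed |

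Protocol 12.3 treats product use, dependence and CYP2A6 in a single sentence. The SAP moves only product use.

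**2. Who is added.** Under SAP 10.2 the product test alone counts as exposure. SAP 10.3 requires randomization, P3P exposure after randomization and a valid non-safety assessment. The Safety population therefore adds mainly (a) testers who were never randomized and (b) randomized subjects with no later P3P exposure.

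**3. Where they land.** Group (a) has no variant and can appear only under Total or overall. The diary starts on Day 1 (SAP 7.3.3), so these subjects have no data in any later period. They also have no Day 1 to Day 29 average, so SAP 12.1.7 cannot place them in an exposure category, although Table 15.2.18.2 is split by that category. Group (b) appears under its own variant.

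**4. Size in the Total column.** The plan has no figure to reproduce. It fixes 60 randomized subjects on an empirical basis, and protocol 5.2 allows replacement until randomization, so the number of testers, u, is open. I assume u = 5, 10 and 15.

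- Missing by construction = u/(60+u): 5/65 = 7.7%; 10/70 = 14.3%; 15/75 = 20.0%.
- A category that truly holds 50% of the 60, with full N as denominator = 50% × 60/(60+u): 46.2%; 42.9%; 40.0%.
- The same category with subjects who have data as denominator: 50% throughout.

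The SAP gives no denominator rule for these tables, so the second line is conditional. Number and percent missing must be reported under SAP 12.1.3, so the first line follows wherever a Total column is produced.

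**5. Size in the variant columns.** With about 30 per arm, one subject in group (b) counted as zero multiplies the mean P3P per day by 29/30 = 0.967. If that subject is treated as missing, the mean does not change. Randomization is on Day -1 and the next use is the supervised single product on site on Day 1, so few such subjects are likely.

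**6. The product-test row.** Table 7 in SAP 7.9 lists the product test as an exposure period, and SAP 12.4 tabulates periods by variant. Every randomized subject had alternated both variants before assignment, using 2 to 6 products. With strict alternation, an even count is half the other variant. With 3 or 5 products, the other variant's share is 1/3 or 2/3, or 2/5 or 3/5. A column headed by the later-assigned variant therefore does not describe what was used.

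**The case against.** The strongest reply has four parts.

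First, SAP 9 bars combined-variant results after baseline. If that rule prevails, these tables have no Total column and the testers drop out of them. This stands as a limit on the effect. But SAP 12.4 explicitly asks for a Total and SAP 12.1.3 for an overall summary, so the plan contradicts itself and the programmer must choose. For the SAP 12.5.4 tables, the overall column rests on SAP 12.1.3 alone.

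Second, a reader might infer that Total percentages are certainly diluted, or that testers would be counted at zero use in the lowest category. The documents support neither. The denominator is not stated, protocol 12.1.4 in general rules out imputing missing data, SAP 12.1.3 includes only available data, and testers never entered the period over which use is averaged.

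Third, a reader might infer that randomized subjects who never used P3P again are wrongly included. They were asked to switch, and keeping them in a product-use summary is defensible. The case for the Randomized population here is that the protocol specifies it, not that these subjects must go.

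Fourth, exposure on the Safety population usefully accompanies the adverse event tables and Table 15.2.25.2, which relates product events to the number of P3P used. That stands, and it is a reason to keep such a table as support. It does not cover the switching tables.

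**Conclusion.** The point holds as an undeclared departure from protocol 12.3 for a secondary objective, with a limited numerical effect. The change of population, its absence from SAP 9, and the mismatch between the SAP 12.4 tables and their listing are plain on the page. The effect is confined to the Total or overall column: a larger N, more missing data, and lower category percentages only if full N is the denominator. The illustrative figures rest on assumed tester counts, and the percentage figures also on an assumed true share of 50%.

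It would be tempting to read this as distorting the comparison between P3P-1mg and P3P-2mg. The documents do not support that: testers belong to no variant, and randomized non-users are probably very few. The endpoint is descriptive, no test depends on it, and the primary PK analysis is unaffected. It is worth correcting because the repair is cheap and two of the tables are topline outputs.

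**What to change.** - Run Tables 15.2.8.1 to 15.2.8.4 for Day 1 onward, and Tables 15.2.18.1 to 15.2.18.8, on the Randomized population. This also gives 15.2.18.8 a population and aligns the tables with Listing 15.1.8.1.
- If an extent-of-exposure table on the Safety population is wanted beside the adverse event tables, keep it as supportive and declare it in SAP 9.
- Reconcile the Total column with SAP 9: either drop it from post-baseline product-use tables or write the exception into SAP 9.
- State the percentage denominator and how subjects without diary data are counted.
- Show the product-test period once, for all testers, with separate counts of P3P-1mg and P3P-2mg used, instead of under the later-assigned variant.

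The cost is edits to SAP 9, 12.4 and 12.5.4 and to the table shells. No new data are needed.

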12.5 Planned Statistical Analyses

12.5.1 Primary Analyses of PK parameters

An analysis of covariance (ANCOVA) will be conducted at Day 30 on background-corrected $AUC_{(0-4h)}$ ($cAUC_{(0-4h)}$) and background-corrected C_{max} (cC_{max}) endpoints in the natural logarithmic scale. The model will include sex and variant as factors and value at Day 1 in the natural logarithmic scale as a covariate. The results of this analysis for each of $cAUC_{(0-4h)}$ and cC_{max} will be presented as geometric least square means and 95% confidence intervals for each variant and least square mean ratio and 95% confidence intervals of P3P-2mg:P3P-1mg ratio.

The same ANCOVA analysis will be performed for the $AUC_{(0-4h)}$ and C_{max} derived using uncorrected concentrations.

LS means for each product will be back-transformed by exponentiation and will be tabulated together with the ratio (P3P-2mg:P3P-1mg) and 95% CI.

In addition, least square mean ratio and 95% confidence intervals of Day 30 versus Day 1 will be provided by variant using an ANOVA model for the difference Day 30 – Day 1 in the natural logarithmic scale endpoints; the ANOVA model will have variant and sex as factors. LS means for each product will be back-transformed by exponentiation.

The geometric CV will also be presented as $CV(\%) = 100\sqrt{(e^{MSE} - 1)}$, where MSE is the mean square error of the fitted model residual.

Descriptive statistics for t_{max} will be provided by P3P variant, the p-value resulting from the non-parametric between-group comparison (Wilcoxon Rank Sum Test) will be reported. The Hodges-Lehman estimate for the between-group difference in median will be reported together with its 95% CI.

Descriptive statistics will be presented by sex (male or female) and by product exposure category.

For t_{max} , descriptive statistics by sex and product exposure will also be provided.

To better understand the impact of the higher than expected T_0 values, a sensitivity analysis of the Background-Corrected and Uncorrected $AUC_{(0-4h)}$ and C_{max} will be performed where data for subjects with their T_0 value $>5\%$ of their C_{max} value will be excluded from the analysis.

The data will be presented in the below outputs:

TFL number	Title
TABLES	
15.2.9.1	Descriptive Statistics of Background-Corrected and Uncorrected Pharmacokinetic Parameters of Nicotine (AUC _(0-4h) and C _{max}) at Day 1 and Day 30 – PK Population
15.2.9.2	Analysis of Background-Corrected and Uncorrected Pharmacokinetic Parameters of Nicotine (AUC _(0-4h) and C _{max}) at Day 30 and at Day 30 relative to Day 1 – PK Population
15.2.9.3	Descriptive Statistics of Background-Corrected and Uncorrected Pharmacokinetic Parameters of Nicotine (AUC _(0-4h) and C _{max}) at Day 1 and Day 30 by Sex – PK Population
15.2.9.4	Descriptive Statistics of Background-Corrected and Uncorrected Pharmacokinetic Parameters of Nicotine (AUC _(0-4h) and C _{max}) at Day 1 and Day 30 by Product Exposure Category – PK Population
15.2.10.1	Descriptive Statistics of Background-Corrected and Uncorrected t _{max} at Day 1 and Day 30 - PK Population
15.2.10.2	Analysis of Background-Corrected and Uncorrected t _{max} at Day 1 and Day 30 – PK Population
15.2.10.3	Descriptive Statistics of Background-Corrected and Uncorrected t _{max} at Day 1 and Day 30 – by Sex - PK Population
15.2.10.4	Descriptive Statistics of Background-Corrected and Uncorrected t _{max} at Day 1 and Day 30 – By Product Exposure Category – PK Population
15.2.11.1	Sensitivity Analysis of Background-Corrected and Uncorrected Pharmacokinetic Parameter of Nicotine (AUC _(0-4h) and C _{max}) at Day 1 and Day 30 – PK Population
FIGURES	
15.3.1.1	Pharmacokinetic Parameters of Nicotine By P3P variant – PK Population
LISTINGS	
15.1.9.1	Listing of Background-Corrected Pharmacokinetic Parameters of Nicotine – PK Population
15.1.10.1	Listing of Background- Uncorrected Pharmacokinetic Parameters of Nicotine – PK Population

Pharmacokinetic Profiles

Geometric mean (95% CI) profiles, spaghetti plots of individual PK profiles for each subject will also be presented by timepoint.

For the analysis and graphical presentation of plasma concentrations, the nominal timepoints will be used. Plasma concentration data will also be listed along with the details of the actual collection times.

TFL number	Title
TABLES	
15.2.12.1	Descriptive Statistics of Background-Corrected Plasma Nicotine Concentration at Day 1 and Day 30 by Timepoint– PK Population
15.2.12.2	Descriptive Statistics of Uncorrected Plasma Nicotine Concentration at Day 1 and Day 30 by Timepoint– PK Population
15.2.12.3	Descriptive Statistics of Background-Corrected Plasma Nicotine Concentration at Day 1 and Day 30 by Timepoint by Sex – PK Population
15.2.12.4	Descriptive Statistics of Background-Corrected Plasma Nicotine Concentration at Day 1 and Day 30 by Timepoint by Product Exposure Category – PK Population
15.2.12.5	Descriptive Statistics of Uncorrected Plasma Nicotine Concentration at Day 1 and Day 30 by Timepoint by Sex – PK Population
15.2.12.6	Descriptive Statistics of Uncorrected Plasma Nicotine Concentration at Day 1 and Day 30 by Timepoint by Product Exposure Category – PK Population
FIGURES	
15.3.2.1	Background-Corrected Plasma Nicotine Concentration-Time Profiles at Day 1 and Day 30- Linear– PK Population
15.3.2.2	Uncorrected Plasma Nicotine Concentration-Time Profiles at Day 1 and Day 30–Linear- PK Population
15.3.2.3	Background-Corrected Plasma Nicotine Concentration-Time Profiles at Day 1 and Day 30- Semi-Log– PK Population
15.3.2.4	Uncorrected Plasma Nicotine Concentration-Time Profiles at Day 1 and Day 30–Semi-Log- PK Population
15.3.2.5	Individual Background-Corrected Plasma Nicotine Concentration-Time Profile at Day 1 and Day 30- Linear– PK Population
15.3.2.6	Individual Uncorrected Plasma Nicotine Concentration-Time Profile at Day 1 and Day 30- Linear– PK Population
15.3.2.7	Individual Background-Corrected Plasma Nicotine Concentration-Time Profile at Day 1 and Day 30- Semi-Log– PK Population
15.3.2.8	Individual Uncorrected Plasma Nicotine Concentration-Time Profile at Day 1 and Day 30- Semi-Log– PK Population
LISTINGS	
15.1.12.1	Listing of Individual Background-Corrected and Uncorrected Plasma Nicotine Concentrations

